5.4.4.3 Diabetes and Glycemia	

Page 2 of 27

	5.4	.4.4 Renal Safety	
		Physical Examination (PE)	
		Vital Signs and Weight	
6	DMC Analyses		
	7 Reference 23		
8	Appendices		
	8.1 A	ppendix 1: Schedule of Events (Subject Visit Schedule)	
		ppendix 2: Adverse Event of Special Interest (AESI)	

Page 3 of 27

Abbreviation or Specialist Term	Explanation
AE	Adverse event
AESI	Adverse events of special interest
ALB	Albumin
ALK-P	Alkaline phosphatase
ALT	Alanine aminotransferase
АроВ	Apolipoprotein B
ASCVD	Atherosclerotic cardiovascular diseases
AST	Aspartate aminotransferase
BMI	Body mass index
BP	Blood pressure
BUN	Blood urea nitrogen
Са	Calcium
CAS	Completer Analysis Set
CEC	Clinical Event Committee
CI	Confidence interval
СК	Creatine kinase
Cl	Chloride
CO 2	Carbon dioxide
CV	Cardiovascular
DBP	Diastolic blood pressure
DMC	Data Monitoring Committee
eCRF	Electronic case report form
EDC	Electronic data capture
eGFR	Estimated glomerular filtration rate
EOS	End of Study
ETC-1002	Bempedoic acid
FDA	Food and Drug Administration
FPFV	First patient first visit
HbA 1C	Glycosylated hemoglobin, Type A 1C
Hct	Hematocrit
HDL-C	High-density lipoprotein cholesterol
HeFH	Heterozygous familial hypercholesterolemia
Hgb	Hemoglobin
hs-CRP	High-sensitivity C-reactive protein
ICH	International Conference on Harmonisation

# **1** List of Abbreviations

Confidential

Page 4 of 27

Abbreviation or Specialist Term	Explanation
IMP	Investigational medicinal product
ITT	Intention-to-treat
IWRS	Interactive web response system
K	Potassium
LDH	Lactate dehydrogenase
LDL-C	Low-density lipoprotein cholesterol
LMT	Lipid modifying therapy
LPLV	Last patient last visit
LS	Least square
MACE	Major adverse cardiac event
МСН	Mean corpuscular hemoglobin
MCHC	Mean corpuscular hemoglobin concentration
MedDRA	Medical Dictionary for Regulatory Activities
MI	Myocardial infarction
Na	Sodium
non-HDL-C	Non-high-density lipoprotein cholesterol
OLE	Open-label extension
Parent study	Study 1002-040
PE	Physical exam
PT	Preferred term
RBC	Red blood cell
SAE	Serious adverse event
SAP	Statistical Analysis Plan
SBP	Systolic blood pressure
SGOT	Serum glutamic oxaloacetic transaminase
SGPT	Serum glutamic pyruvic transaminase
SI	International system of units
SOC	System organ class
SP	Safety population
ТВ	Total bilirubin
TC	Total cholesterol
TEAE	Treatment-emergent adverse event
TESAE	Treatment-emergent serious adverse event
TG	Triglycerides
ULN	Upper limit of normal
WBC	White blood cell
WHO	World Health Organization

Confidential

Page 5 of 27

# 2 Introduction

The purpose of this document is to describe the statistical methods, data derivations and data summaries to be employed in ETC-1002-050. The preparation of this statistical analysis plan (SAP) has been based on International Conference on Harmonisation (ICH) E3 and E9 Guidelines and in reference to Protocol ETC-1002-050 (Protocol Amendment 2, 15Jan2018).

The SAP will supersede the protocol in the event of any differences between the two documents in the plans for data analysis, and the protocol will be amended if appropriate. The SAP will be included as an appendix in the clinical study report for this protocol.

# **3** Study Objectives and Endpoints

## 3.1 Objectives

- The primary objective for this study is to characterize the safety and tolerability of long-term administration of bempedoic acid (ETC-1002) 180 mg
- The secondary objective is to characterize the efficacy of long-term administration of bempedoic acid 180 mg/day as assessed by changes in low-density lipoprotein cholesterol (LDL-C), high-density lipoprotein cholesterol (HDL-C), non-high-density lipoprotein cholesterol (non-HDL-C), apolipoprotein B (ApoB), total cholesterol (TC), triglycerides TG, and high-sensitivity C-reactive protein (hs-CRP) in patients with hyperlipidemia

## 3.2 Endpoint

## Primary Endpoint (Safety)

• The primary endpoint for this study is patient incidence of treatment-emergent adverse events (TEAEs)

### **Secondary Endpoints (Efficacy)**

- Percent change from baseline in LDL-C at Weeks 52 and 78
- Change from baseline in LDL-C at Weeks 52 and 78
- Percent change from baseline in non-HDL-C at Weeks 52 and 78
- Percent change from baseline in TC at Weeks 52 and 78
- Percent change from baseline in ApoB at Weeks 52 and 78

#### Confidential

Page 6 of 27

Page 108 of 129
Version 1.3, Dec 04, 2019 Statistical Analysis Plan

- Percent change from baseline in hs-CRP at Weeks 52 and 78
- Percent change from baseline in TG at Weeks 52 and 78
- Percent change from baseline in HDL-C at Weeks 52 and 78

### **Other Safety Endpoints**

- Laboratory Results
- Physical Measurements
- Vital Signs
- Hepatic Safety
- Musculoskeletal Safety
- Diabetes and Hyperglycemia
- Renal Safety
- Neurocognitive Events
- Clinical Endpoints

#### 3.2.1 Adverse Events

The evaluation of adverse events (AEs) will include only incidence of TEAEs, defined as AEs that begin or worsen on or after the date of first dose of study drug administration in open-label extension (OLE) period and until 30 days after last dose of study drug. AESI will be examined further (See Section 5.4.2 for more information).

Clinical endpoints (details see section 4.2) will be collected and adjudicated by an independent Clinical Events Committee (CEC). Clinical endpoints will also be reported as AEs.

#### **3.2.2** Clinical Safety Laboratories

The evaluation of clinical safety laboratories, including blood hematology, chemistry, coagulation, and urinalysis will be based on the observed values. Observed values, change from baseline, and percent change from baseline of both the parent study and OLE study will be summarized for all the scheduled post-baseline visits.

#### 3.2.3 Vital Signs

The evaluation of vital signs (including heart rate, systolic blood pressure, and diastolic blood pressure, and weight and BMI) will be based on the observed values. The summary of the observed values and change from baseline will be performed for all the scheduled visits based on the baseline of the parent study and OLE study. Baseline height will be summarized and will be used in the BMI calculations over time.

Confidential

Page 7 of 27

Page 109 of 129

#### 3.2.4 Physical Exam

Listings of PE data will include only those records where the body system at the baseline PE was normal, but the body system at a post-baseline PE was marked as 'Change from previous exam, clinically significant.'

#### 3.2.5 Lipids

After enrollment, patients will return to clinic at Weeks 12, 52, 78/EOT, and 82/EOS. Clinical laboratory samples will be collected and analyzed for calculated LDL-C and lipid and cardiometabolic biomarkers including non-HDL-C, HDL-C, TC, ApoB, and TG at baseline and all clinic visits for evaluation of bempedoic acid effects on lipids and cardiometabolic parameters.

## 4 Study Design

## 4.1 Study Design

This is a multicenter OLE study designed to assess the long-term safety and efficacy of bempedoic acid (ETC-1002) 180 mg. All patients will receive open-label bempedoic acid 180 mg for up to 1.5 years after rolling over from the parent study (Study 1002-040) followed by a follow-up period off study drug for 4 weeks. Investigators, site staff, patients, and the study team will be masked to study lipid levels until the Week 12 study visit, after which time lipid values will be made available.

An independent expert Data Monitoring Committee (DMC) will formally review accumulating unblinded safety and efficacy data from this and other ongoing studies of bempedoic acid. A blinded independent expert Clinical Events Committee (CEC) will adjudicate designated clinical endpoints across the program, including all major adverse cardiac events (MACE) and non-MACE endpoints defined as: cardiovascular (CV) death (MACE), non-CV death (non-MACE), nonfatal myocardial infarction [MI] (MACE), nonfatal stroke (MACE), hospitalization for unstable angina (MACE), coronary revascularization (MACE), noncoronary arterial revascularization (non-MACE), and hospitalization for heart failure (non-MACE) using standardized definitions. Any clinical endpoints that meet serious adverse event (SAE) criteria will be reported as SAEs as well as a clinical endpoint.

The study will be conducted at approximately 125 clinical sites in the United States, Canada, Germany, Netherlands, Poland, and United Kingdom. The study will end when the last randomized patient completes their last study visit (last patient last visit [LPLV] for last randomized patient). The estimated overall duration of the study (first patient first visit [FPFV] to LPLV) is approximately 2.5 years.

Confidential

Page 8 of 27

#### Figure 1. Study 1002-050 Study Design

## 4.2 Study Treatments and Assessments

Day 1 for this study should occur on the same day as the end of study visit for the parent study (1002-040). Patients who provide informed consent will be eligible to enroll in the study.

The schedule of study events is provided in Appendix 1. However, a patient can be seen at any time for reasons of safety.

The investigational products were listed in Table 1 below:

Investigational Medicinal Product
Bempedoic acid
Film-coated tablets
180 mg
100-count bottle with screw on, child proof cap
Oral, daily with or without food

Table 1:	Investigational Medicinal Product	ts
----------	-----------------------------------	----

Page 9 of 27

Study drug should be taken once a day (once every 24 hours) at approximately the same time every day and may be taken with or without food. Patients will fast (no food or drink, other than water) for a minimum of 10 hours prior to collection of all laboratory samples.

Please see Pharmacy Manual for detailed storage requirements and instructions.

Patients who withdraw from investigational medicinal product (IMP) treatment will be asked to continue to be followed for safety using the protocol-specified visit schedule and procedures. For details of study assessments, see Appendix 1: Schedule of Events (Subject Visit Schedule).

An independent expert Data Monitoring Committee (DMC) will formally review accumulating unblinded safety and efficacy data from this and other any ongoing studies of ETC-1002. All clinical endpoints, including all major cardiac events (MACE) and non-MACE endpoints defined as: CV death (MACE), non-CV death (non-MACE), nonfatal myocardial infarction (MI) (MACE), nonfatal stroke (MACE), hospitalization for unstable angina (MACE), coronary revascularization (MACE), non-coronary arterial revascularization (non-MACE), and hospitalization for heart failure (non-MACE), will be adjudicated by an independent blinded expert Clinical Events Committee (CEC), using standardized definitions. Any clinical endpoints that meet serious adverse event (SAE) criteria will be reported as SAEs.

## 4.3 Randomization and Blinding

Randomization is not applicable for this OLE study.

Laboratory results for lipid panel and hs-CRP will be masked to investigators, patients, and the study team until the Week 12 visit is completed. All site staff involved with this trial should refrain from obtaining lipid panels between date of last study medication (bempedoic acid or placebo) dose at end of parent study Week 52 (Visit T7) and Week 12 in this OLE trial.

## 4.4 Sample Size Justification

The number of patients entering this study will depend on the number of patients completing Study 1002-040 and their willingness to enroll.

## 4.5 Interim Analyses, Final Analyses, and Unblinding

An interim analysis will be conducted in 2H 2018 in order to provide safety assessment to support NDA submission. Another interim analysis for Day120 safety update will be approximately 120 days after the NDA cutoff. The endpoints and analyses are the same as those defined in final analysis if applicable.

The final analysis will be performed after the database is locked. Confidential

Page 10 of 27

Page 112 of 129

## 4.6 Change from Planned Analyses in Protocol

There is no change from planned analyses for this study.

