12.4. Primary Endpoint

All safety endpoints will be summarized using the SP.

The MedDRA will be used to code all AEs to a system organ class (SOC) and a preferred term.

The patient incidence of all TEAE, SAEs, related AEs, AEs leading to withdrawal of IMP, fatal AEs, and AESI will be tabulated by system organ class and preferred term in descending order of frequency. If appropriate, exposure-adjusted patient incidence rate will also be provided.

Adverse events occurred in the parent study and continued into the OLE study without change in severity will be captured in the parent study only.

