12.6. Other Safety Endpoints

Laboratory Results

Actual value or change from baseline (where appropriate) in clinical safety laboratories, including hematology, blood chemistry, HbA_{1C}, glucose, and urinalysis will be summarized at each scheduled visit.

Shift tables for selected safety laboratory parameters will be provided.

Physical Measurements

Height and weight will be summarized at each scheduled visit.

Vital Signs

Hear rate, SBP and DBP will be summarized at each scheduled visit.

Hepatic Safety

Actual value and change from baseline in liver-associated enzymes and TB will be summarized at each visit. In addition, the number and percent of patients with normal vs. abnormal values for ALT, AST, and TB will be summarized by their baseline and postbaseline status. Hy's law criteria (>3 × ULN for either ALT or AST, with accompanying TB >2 × ULN or patient's baseline) will also be applied to the data; any potential Hy's law cases will be listed separately. In the case of patients with Gilbert's disease, TB will be fractionated and the determination of $2 \times ULN$ based upon direct (conjugated) bilirubin. For patients with Gilbert's Disease $2 \times$ the conjugated bilirubin will be used as the criterion.

Musculoskeletal Safety

Adverse events of muscle-related symptoms will be summarized. Creatine kinase levels will be summarized by the value and change from baseline in the value, by visit. In addition, the number and percent of patients with normal vs. abnormal CK values will be summarized by their baseline and post-baseline status.

Diabetes and Hyperglycemia

Cases of new onset of diabetes will be recorded as AEs and will be summarized using the appropriate SOC. These events will be summarized by severity and relationship to study drug. Glucose and HbA_{1C} will be monitored at baseline and at Weeks 12, 52 and 78, and be summarized by history of diabetes.

Renal Safety

Baseline eGFR will be summarized for actual value and for baseline eGFR categories. Shift tables of eGFR category from baseline over the study, will be provided. Shift tables of urine protein (negative/positive) from baseline over the study, will be provided. Values of CK will be summarized by baseline eGFR category.

Neurocognitive Events

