Neurocognitive events will be identified and evaluated by routine safety monitoring of PE findings and AEs. Summarization of neurocognitive events will occur using prespecified MedDRA terms and will be performed by SOC and PT, severity, and relationship to study drug.

Clinical Endpoints

Clinical endpoints using standardized definitions will be adjudicated by an independent blinded expert CEC for all ongoing Phase 3 studies in the bempedoic acid program. Investigator-reported clinical endpoints and adjudicated clinical endpoints will be summarized by event type. Additional details regarding the clinical endpoints and their definitions will be included in CEC Charter.

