#### 5.4.1 Adverse Events (AEs)

AEs will be coded using the Medical Dictionary for Regulatory Activities (MedDRA) Version 20.1 or later and will be categorized by system organ class (SOC) and preferred

Confidential

Page 15 of 27

Page 117 of 129

term (PT). Summary tables will focus on TEAEs; however, listings will include all AEs (with non-TEAEs flagged). An additional AE listing will be provided for AEs occurred during rollover period.

In summary tables, TEAEs will be counted as "Not Related" if relationship to study drug was recorded as 'Not Related' or "Unlikely". Events will be counted as "Related" if relationship to study drug was recorded as 'Possible', 'Probable', 'Definite' or if relationship to study drug is missing.

The severity of the AE will be characterized as mild, moderate, or severe, to the following definitions:

- Mild: Events are usually transient and do not interfere with the patient's daily activities
- Moderate: Events introduce a low level of inconvenience or concern to the patient and may interfere with daily activities
- Severe: Events interrupt the patient's usual daily activity, are incapacitating with inability to do usual activities, or significantly affect clinical status and warrant intervention and/or close follow-up

Overviews of TEAEs will include total number of TEAEs, and patient incidence of TEAEs, TESAEs, treatment-related TEAEs, treatment-related TESAEs, IMP withdrawal due to TEAEs, TEAEs with fatal outcome. Individual TEAE summary will be presented by previous treatment group in parent study and overall containing the following counts and percentages for:

- patients with TEAEs by SOC and PT
- patients with TEAEs by PT
- patients with TEAEs by SOC, PT, and maximum severity
- patients with treatment-related TEAEs
- patients with treatment-related TEAEs by PT
- patients with treatment-related TEAEs by SOC and PT
- patients with treatment-emergent serious adverse events (TESAEs) by SOC and PT
- patients with TESAEs by PT
- patients with TESAEs by SOC, PT, and maximum severity
- patients with treatment-related TESAEs
- patients with treatment-related TESAEs by SOC and PT
- TEAEs leading to withdrawal of IMP by SOC and PT
- fatal TEAEs by SOC and PT

Preferred terms for TEAEs that occurred in more than 1% of subjects overall will be plotted using the overall group. This plot will be repeated for TESAEs in the overall group.

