#### Confidential

Page 16 of 27

In addition, summary tables will be provided, by prior treatment group and overall, for the number and percent of patients experiencing:

- adjudicated major adverse cardiovascular events and mortality (MACE) by event type
- non-CV deaths (non-MACE),
- nonfatal myocardial infarction [MI] (MACE),
- nonfatal stroke (MACE),
- hospitalization for unstable angina (MACE),
- coronary revascularization (MACE),
- noncoronary arterial revascularization (non-MACE),
- hospitalization for heart failure (non-MACE) using standardized definitions.

The TEAE, treatment-related TEAE, TESAE, and AESI summaries by SOC, PT and maximum severity will be provided for relevant subgroups described in 5.2.5 with the exception of baseline LDL category.

The AE overview summaries will count a patient at most once in each AE category (at the "highest/most extreme" designation of each category regardless of preferred term) and percentages will be based on the total number of patients in the safety population.

In addition to a comprehensive listing of all AEs (with non-TEAEs flagged), separate listings will be generated for serious adverse events, TEAEs resulting in withdrawal of study drug, and TEAEs with a fatal outcome, investigator reported major adverse cardiovascular events and mortality, and adjudicated major adverse cardiovascular events and mortality.

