#### **5.4.4 Laboratory Evaluations**

Continuous laboratory parameters (serum chemistry, hematology, coagulation (only for those patients receiving anti-coagulation), urinalysis, urinalysis [microscopic]) listed in Table 4 will be summarized in conventional unit and SI unit using descriptive statistics at each scheduled visit starting from the baseline of the parent study. The similar completer analysis set approach for efficacy analysis described in section 5.3 will be used for selected parameters. Missing values for any of the laboratory evaluations will not be imputed; that is, only observed case data will be used.

Fasting serum glucose and HbA1c will be summarized using descriptive statistics for the observed value, change from baseline, and percent change from baseline at each scheduled visit by history of diabetics.

Categorical urinalysis data will be listed, but will not be summarized.

As part of the AESI evaluation, below safety lab abnormality will be summarized by treatment group. All post-baseline lab values during the on-treatment period are being considered. Further details are provided in Section 5.4.6.1 through 5.4.6.4.

- ALT or AST (>  $3 \times$  Upper limit of normal (ULN) and > $5 \times$  ULN)
- Total bilirubin (TB) (> 2 × ULN)
- Potential Hy's Law case: (ALT and/or AST > 3 × ULN with concurrent TB > 2 × ULN)
- CK (>  $5 \times$  ULN) and (> $10 \times$  ULN)
- Fasting Serum Glucose (mg/dL) ( $\leq$  50, and  $\geq$  126) by history of diabetics
- HbA1C ( $\geq$  6.5%) by history of diabetics
- Creatinine (change from baseline for >1 mg/dL)
- eGFR (< 15 mL/min/1.73m^2, 15 29 mL/min/1.73m^2)
- Hgb (g/dL) (decrease from baseline for  $\geq 2$  g/dL)
- Hgb (< 8 g/dL)

The number and percentage of patients with the following laboratory abnormalities will be summarized by the parent study baseline statin intensity, previous treatment group in the parent study, and overall in the OLE study:

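### SAP v1.3 section 4.6 declares no change from the protocol's analyses, yet one endpoint summary has become a listing, SAE and fatal-event tables are narrowed, and the time scope for adjudicated endpoints needs stating

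*SAP*

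**What the plan says.** SAP v1.3 section 2 refers to protocol Amendment 2 of 15 January 2018 and gives the SAP precedence wherever the two differ on analysis. Section 4.6 then states: "There is no change from planned analyses for this study". The v1.3 heading of 4.6 names the protocol as the comparator, which the same heading in v1.0, v1.1 and v1.2 did not. The relevant pairs are:

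- **Investigator-reported endpoints.** Protocol 12.6: "Investigator-reported clinical endpoints and adjudicated clinical endpoints will be summarized by event type". In SAP v1.3 5.4.1 the event-type tables start from adjudicated MACE. Investigator-reported events are named only among the separate listings: "investigator reported major adverse cardiovascular events and mortality, and adjudicated major adverse cardiovascular events and mortality".
- **SAEs and fatal events.** Protocol 12.4: "The patient incidence of all TEAE, SAEs, related AEs, AEs leading to withdrawal of IMP, fatal AEs, and AESI will be tabulated". SAP v1.3 5.4.1 has instead "patients with treatment-emergent serious adverse events (TESAEs) by SOC and PT" and "fatal TEAEs by SOC and PT".
- **Urine protein.** Protocol 12.6: "Shift tables of urine protein (negative/positive) from baseline over the study, will be provided". The v1.3 renal section (5.4.4.4) covers eGFR and creatinine only, and 5.4.4 says: "Categorical urinalysis data will be listed, but will not be summarized".
- **Adjudicated endpoints.** SAP v1.3 5.4.3 limits the summary to treatment-emergent events. The list of event tables in 5.4.1 gives no time limit, and neither does protocol 12.6. Section 3.2.1 closes the treatment-emergent window 30 days after the last dose.

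**The concern.** Safety is the primary objective, and 4.6 is where a reader checks whether the safety outputs still match the protocol. Because the SAP takes precedence, an output narrowed or left out of v1.3 can lapse while 4.6 tells the reader that nothing has changed.

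The time scope carries the substance. A patient may stop treatment because of harm and remain in follow-up. If every table ends 30 days after the last dose, a later MACE or a death from a later event is absent from the summaries and has to be rebuilt from listings.

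**Working it through.** **Setting the texts side by side.** No figure stated in the plan is at issue, so the first part is a comparison of wording.

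1. *Investigator-reported endpoints.* SAP v1.0 5.4.1 had a summary table for these next to the adjudicated one. SAP v1.3 has only the listing. A listing is not a summary by event type, so 4.6 is wrong on this item.
2. *SAEs and fatal events.* Protocol 12.4 names TEAEs, SAEs and fatal AEs as separate items and states no treatment-emergent limit for the last two. Serious events were already tabulated as treatment-emergent in v1.0. For fatal events the narrowing is new in v1.3: v1.2 still had a fatal-AE table and a fatal-event listing without that limit, and v1.3 restricts both. A death from an event starting after the window stays in the all-AE, SAE and adjudicated listings.
3. *Urine protein.* SAP v1.0 had both the sentence saying categorical urinalysis is not summarized and an express urine-protein shift table. SAP v1.2 kept the sentence and had no urine-protein text in its renal section. The Day 120 addendum, written under v1.2, nevertheless lists urine-protein shifts as Tables 14.3.6.3.1 and 14.3.6.3.2. SAP v1.3 again has the sentence and no table. Silence is established; removal is not.
4. *Adjudicated endpoints.* In v1.3, 3.2.1 confines AE evaluation to TEAEs and says clinical endpoints are also reported as AEs. Section 5.4.1 says its tables concentrate on TEAEs, and 5.4.3 names the limit. Together they point to a treatment-emergent scope, but the 5.4.1 list does not say so.

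**Days of follow-up outside the window.** Inputs: target days 84, 364, 546 and 574 (visit-window table, SAP v1.3 5.1); the 30-day tail (SAP v1.3 3.2.1); the +14-day allowance for Week 82 (protocol Appendix 1). The last dose is taken to fall on the visit's target day.

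Window closes = last-dose day + 30. Days outside = max(0, end of follow-up − window close).

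| Last dose | Window closes | Follow-up ends | Days outside |
|---|---|---|---|
| Day 84 (Week 12) | 84 + 30 = 114 | 574 | 574 − 114 = 460 (460/574 = 80%) |
| Day 364 (Week 52) | 364 + 30 = 394 | 574 | 574 − 394 = 180 (180/574 = 31%) |
| Day 546 (completer) | 546 + 30 = 576 | 574 | 0 |
| Day 546, late Week 82 visit | 576 | 574 + 14 = 588 | 588 − 576 = 12 |

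The first two rows apply only to patients who accept continued follow-up (protocol 9.3.1 and 9.3.2, with consent). Protocol 9.2.7 and Appendix 1 footnote 2 also place the final visit 4 weeks after the last dose for early withdrawals. A patient who leaves at that visit has 28 days of follow-up, inside the 30-day window, or 28 + 14 − 30 = 12 days outside it if the visit is late.

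Non-serious AEs are unaffected, because protocol 11.1.3 collects them only to 30 days after the last dose. The gap concerns SAEs, deaths and clinical endpoints.

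**The case against.** The strongest reply is that this is mostly wording. Protocol 11.1.7 leaves the definition of TEAEs to the SAP, and every SAP version confines AE evaluation to them. The section specific to adjudicated endpoints states the limit, and the Day 120 table titles follow it. TEAE status depends on onset, so a late death from an event that began inside the window still counts as a fatal TEAE. Investigator-reported endpoints that are treatment-emergent remain in the SOC and preferred-term tables, and all events are listed. Much of this stands: no data are lost, and the scope can be inferred. It does not rescue 4.6. One promised summary is now a listing, and the fatal-event table was narrowed between v1.2 and v1.3 without being declared.

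A reader might also infer more than the documents support:

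- *That the urine-protein table has been dropped.* The v1.0 text and the Day 120 list show that neither the general sentence nor silence in the renal section excluded it. SAP v1.3 4.5 also says the interim analyses match the final ones where applicable.
- *That completers lose 28 days of SAE reporting.* SAE reporting does run to Day 604 (574 + 30), and 604 − 576 = 28. Those days fall after the last scheduled visit, and a table closing at Week 82 would not recover them.
- *That confidence intervals, the efficacy analysis set and exposure adjustment are broken commitments.* SAP v1.3 5.1 drops categorical estimates from the interval provision, but the protocol promised intervals only for selected endpoints and never named AE incidence. Efficacy uses the safety population rather than the all-enrolled set of protocol 12.3, but the synopsis already defines the full analysis set as dosed patients. Protocol 12.4 foresees exposure-adjusted incidence only where appropriate. None of these has a material effect as a departure.

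**Conclusion.** The declaration in 4.6 is inaccurate. Two departures are clear: the investigator-reported summary has become a listing, and the SAE and fatal-AE tabulations are narrowed to treatment-emergent events. The urine-protein shift table is unconfirmed. The scope for adjudicated endpoints is probably treatment-emergent but is not stated consistently; since the protocol sets no window for those tables, this is an ambiguity rather than a broken promise.

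The consequence falls on early stoppers who stay in follow-up: 460 days outside the tables after stopping on Day 84 and 180 after stopping on Day 364, if followed to Day 574. Completers have 0 to 12 days outside through the Week 82 visit. These figures assume a last dose on the target day and a treatment-emergent reading of 5.4.1. The number of events affected cannot be derived, because the documents give no stopping rate, acceptance of follow-up or event rate. The events stay in the listings, so the weakness is in reporting, not in data collection. In a study whose primary purpose is long-term safety it should be corrected.

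**What to change.** - Rewrite 4.6 to list the changes with reasons: the investigator-reported summary, and the narrowing of the SAE and fatal-event tables. The interval and analysis-set differences can be noted there in a line each.
- Restore the event-type summary of investigator-reported endpoints.
- Confirm whether the urine-protein shift table will be produced, and reconcile the answer with the urinalysis sentence in 5.4.4.
- State one time scope for adjudicated endpoints in both 5.4.1 and 5.4.3.
- Beside the treatment-emergent table, add one of all adjudicated endpoints and deaths collected through end of study.
- Optionally, carry the Day 120 addendum's definition of exposure-adjusted incidence into the final analysis, beside the percentages.

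The cost is SAP wording and a few extra tables from data already collected. Study conduct does not change.
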